**1. BACKGROUND**

**1.1. Rationale for household water treatment**

Diarrhoeal diseases kill an estimated 1.8 million people each year (WHO 2005). Children under 5 years of age are especially vulnerable, representing more than 90% of this disease burden. Among children under 5 in developing countries, diarrhoeal diseases account for 21% of all deaths (Parashar 2003). Although diarrhoea accounts for more than 4.2% of the worldwide disease burden (WHO 2004), it is largely preventable. Ingestion of unsafe water, along with inadequate availability of water for hygiene and a lack of sanitation, account for 88% of deaths from diarrhoea (WHO 2002). Expanding access to safe drinking water is among the chief priorities expressed in the UN's Millennium Development Goals (MDGs) (WHO/UNICEF 2008).

An estimated 884 billion people lack access to safe water (WHO/UNICEF 2008). The problem is particularly acute among rural and urban slum populations, many of which suffer from increased exposure due to poor sanitation. Even systems that qualify as "improved" under the WHO/UNICEF assessment, such as protected wells and gravity systems, often deliver highly contaminated water due to improper maintenance or operation (RDWQA 2006). Storing water in the home, a common practice due to distant or unreliable water supplies, is also a source of diarrheagenic pathogens (Wright 2004). As a result, the WHO has encouraged the development and use of improved point-of-use water treatment at the household level (WHO 2007). These interventions were to be an effective and cost-effective means of preventing diarrhoeal and other waterborne diseases (Fewtrell 2005, [name] 2007).

In order to ensure the responsible deployment of such interventions, the WHO recommends that any products designed to treat water at the household level undergo independent testing to assess their microbiological effectiveness and health impact. The double-blinded, randomised, placebo-controlled trial is the gold standard of epidemiological evidence.

We propose to conduct such a trial to assess the impact of in-home chlorination on diarrhoeal disease among children under five in India. With nearly 400,000 deaths of children each year from diarrhoeal diseases, India alone accounts more than 20% of the worldwide mortality associated with diarrhoea (Unicef 2009). Despite considerable progress toward the MDG water target, large portions of the population, particularly in rural settings, still lack access to improved water supplies (WHO/UNICEF 2008). This population could therefore benefit from safe and effective household water treatment. Much of that population lives on less than \$1 or \$2 per day, rendering higher-cost solutions such as filters prohibitive; a simple, low-cost chlorine solution may be most appropriate in India.

The intervention consists of dichloroisocyanurate (NaDCC) (brand name "Aquatabs"). The tablets present certain cost, logistical and other advantages over other chlorine sources suitable for household use. While long used by UNICEF and others in emergency response, NaDCC has now been approved by the WHO and USEPA for routine treatment of drinking water.

**1.2. Previous Field Trials**

In 2006, [name] and colleagues conducted a four-month double-blinded, randomised, placebo-controlled trial among 100 householders within an informal urban settlement in Bangladesh to assess the microbiological effectiveness of NaDCC tablets ([name] 2007). Monthly samples of stored drinking water from intervention households were significantly lower in the thermotolerant coliforms (TTC) than those of control households (geometric mean 2.8 (95%CI: 2.2, 3.6) versus 604.1 (95%CI: 463.2, 787.9),  $P < 0.0001$ ). While none of the 191 samples from the control group met WHO guidelines for zero TTC/100ml, 61.7% samples from the intervention households met such benchmark. All 188 samples from intervention households were positive for residual free chlorine (compared to none of the control household samples), suggesting that householders consistently used the tablets.

The US Centers for Disease Control and Prevention (CDC) subsequently conducted a double-blinded RCT to determine the health impact of daily use of NaDCC tablets for household drinking water treatment in peri-urban Ghana (Jain 2010). They randomized 240 households (3,240 individuals) to receive either NaDCC or placebo tablets. All households received a 20-liter safe water storage vessel. Over 12 weeks, 446 diarrhea episodes (2.2%) occurred in intervention and 404 (2.0%) in control households ( $p=0.38$ ). Residual free chlorine levels indicated appropriate tablet use. *Escherichia coli* was found in stored water at baseline in 96% of intervention and 88% of control households and at final evaluation in 8% of intervention and 54% of control households ( $p=0.002$ ). NaDCC use did not prevent diarrhea but improved water quality. However, diarrhea rates were low and water quality improved in both groups.

The investigators concluded that a follow-up health impact study is warranted. Previous double-blinded trials of household-based water treatment interventions conducted in low-income settings also reported no protective effect on diarrhoeal disease (Kirchoff 1985; Austin 1993). However, each of these studies were conducted under circumstances that raised questions about their results ([name] 2006). This was also true of the CDC trial in Ghana. There the microbiological water quality was comparatively high, so that the difference in faecal contamination between intervention and control groups was relatively low. Moreover, as the investigators acknowledged, the safe water storage vessels may have been protective. Improved storage vessels have been shown to minimize the recontamination of drinking water in the home, and thus reduce exposure to diarrhoeagenic agents (Wright 2004). Improved vessels alone have been associated with a 31% reduction in diarrhoeal disease (Roberts 2001). Thus, the study was essentially a comparison between two interventions rather than an intervention and control. In this respect, it may not have had sufficient statistical power to detect a difference in diarrhoea incidence between the two groups.

## **2. STUDY OBJECTIVES**

The primary objective of the study is to evaluate the efficacy of NaDCC tablets in preventing diarrhoea among children under 5 years of age. The secondary objectives of the study are to measure (i) the impact of the intervention on diarrhoea among study participants of all ages (ii) the impact on weight gain among children <5 years (WAZ is proposed as a proxy for diarrhoea) (iii) the efficacy of the tablets to improve the microbiological quality of drinking water (iv) the extent to which the tablets are used correctly and consistently by the study population (v) the acceptability of intervention for potential long-term use, (vi) impact on school absenteeism (vii) the cost-effectiveness of the intervention.

## **3. METHODS**

The epidemiological design is a parallel double-blinded, randomised, placebo-controlled trial intended to assess the efficacy of NaDCC tablets in reducing diarrhoea among children <5 years over a twelve-month follow-up period.

### **3.1. Pilot phase**

The pilot study will be carried out in one village that will not be part of the actual trial and will involve approximately 100 households with children <5. We will conduct formative research using methods such as focus group discussions and in depth interviews to gain an understanding of local perceptions and practices with regards to water, hygiene and sanitation, and investigate local terminologies for diarrhoea. Households will be explained the objectives of the pilot study. Those willing to participate will be asked to give consent in writing prior to enrollment. Participating households will be randomly allocated to one of two groups. Like in the actual trial, half will receive the active tablets and the other half will receive the placebo. Each household will be followed up for a month. During that period, data collection tools will be piloted. This study will also allow us to confirm the suitability of the area according to key study parameters, explore use and acceptability of the tablets among the target population (chlorine dosage, acceptability of taste etc.) and evaluate the effectiveness of blinding. At the end of the month, in-depth interviews will be conducted with a sample of households to assess whether blinding was successful and if not, identify the reasons why. This will be complemented by a cross-sectional survey asking each mother or primary care giver to guess which tablets they have received. At the end of the pilot phase, a decision to proceed with the larger trial will be made if results show high acceptability and high level of use and if blinding of the intervention is found to be successful.

### **3.2. Site selection**

The study will be conducted in both rural and urban communities in the State of Orissa, India. Study sites will be selected based on the following parameters: (i) most households in the community relying on surface water or other unimproved water supplies with mean thermo tolerant coliforms counts of 500 per 100ml or above (ii) low percentage of the population regularly treating their water before drinking it in some microbiologically effective manner (e.g. boiling); (iii) the community has sufficient quantity and access to water supplies, so that major deficiency is microbiological water quality; (iv) the host organization has on-ground staff and other logistical support (v) the population and community leaders desire to participate in the Study (vi) The site is easily accessible even during the rainy season.

### **3.3. Enrolment and baseline**

A community meeting will be held in each selected village to explain the objectives of the study. For each village, a census of all households will be obtained. Households are eligible to participate in the study if they have at least one child less than five years of age and live permanently in the study area. The age of the child at enrollment will be checked against vaccination records when available. Informed consent will be sought from the heads of the households prior to enrolment. A baseline survey will be undertaken to collect information on demographics, socio-economic characteristics, and water, hygiene and sanitation conditions and practices. The analysis of the baseline data will allow verifying that the two groups are balanced in terms of factors that may influence the outcome of interest.

### **3.4. Randomisation and blinding**

Following baseline, households will be randomly assigned to one of the two groups. Randomisation will be conducted by a member of staff that is neither involved in the delivery of the intervention, nor in the data collection or analysis of the data. Randomisation will be stratified by village and will be done using a computer generated random sequence. The field team involved in the evaluation of the intervention will be different from the team delivering it. The evaluation team will be divided into two groups. One team will be responsible for conducting health surveys and anthropometric measurements. Another team will be responsible for water testing and the evaluation of compliance. During the whole duration of the study, the allocation sequence will be kept hidden from the distributors, the evaluation team and the data analysis team.

### **3.5. The Intervention**

Aquatabs are tablets formed from sodium dichloroisocyanurate (NaDCC) and an effervescent base. Widely used for decades in household and commercial laundry bleaches, scouring powders and industrial and recreational water disinfection, NaDCC has recently found applications ranging from sanitizing medical instruments to cleaning of baby bottles and contact lenses. For more than 30 years, Aquatabs have been used for the emergency treatment of water. Its widespread use in non-emergency household water treatment applications began after acceptance of the chlorinated isocyanurates by the United States Environmental Protection Agency (USEPA), WHO and the Food and Agriculture Organization of the United Nations for the routine treatment of drinking water. NaDCC may also offer certain other advantages over sodium hypochlorite in terms of safety, shelf life, up-front cost and convenience, although these have not yet been shown to impact coverage or uptake ([name] & Edmondson 2006).

Chlorine tablets such as Aquatabs may present a unique opportunity for blinding a household water treatment intervention in low-income settings. Tablets can be manufactured with the effervescent base and no NaDCC and packaged in a manner identical to Aquatabs. Other blinded trials conducted in low-income settings used liquid sodium hypochlorite that may have been noticeable to study participants due to the strong odour of the agent (Kirchoff 1985; Austin 1993). However, prior field trials of Aquatabs showed no evidence that intervention and control populations could detect whether they were using the tablets containing NaDCC (Jain 2010).

Each participating household will be provided with sufficient supplies of Aquatabs or placebos free of charge. Supplies of tablets at the household will be counted by the distributors every two weeks during their visit and topped off to cover the following two weeks. Households will also receive instructions on the use of the same in accordance with the manufacturers instructions and PSI's experience. Consistent with its normal practices, representatives of PSI will make regular visits to participating communities to ensure that they have adequate supplies. The study participants will be advised prior to the commencement of the study that half of the study households will receive a placebo. For this reason, they will be encouraged to continue

to follow their existing water treatment and handling practices and not to take any additional risk with respect to their drinking water management that might increase their exposure.

### **3.6. Outcome assessment**

#### **3.6.1. Diarrhoea morbidity**

The primary outcome is longitudinal prevalence of diarrhoea, which is the number of days ill over the total number of days under observation. Longitudinal prevalence is chosen because it is reported to be closely associated with mortality (Morris 1996). The follow-up will be conducted monthly over 12 months. At each visit, the mother or primary care giver will be asked questions about diarrhoea today, yesterday and the day before yesterday for the child and for each family member who is absent at the time of visit. Diarrhoea will be defined using the WHO definition of three or more loose stools passed within a 24-hour period. The pilot will help identifying the local terms that most closely match that definition. Children found to suffer from diarrhoea will be given oral rehydration sachets and instructions on how to use them. If required, they will be referred to the closest community health centre to receive medical care free of charge.

#### **3.6.2. Weight-for-age Z score (WAZ)**

During health surveys, weight will be recorded for each child less than five years of age. Recent analyses suggest that there is a very strong association between weight-for-age Z score (WAZ) and diarrhoea over the last two weeks, which indicates that WAZ may be a good marker for recent diarrhoea (Schmidt 2009). Therefore, WAZ measured repeatedly in each child will be used as a proxy indicator of diarrhoea. WAZ will be measured according to a standard procedure and scales to minimise measurement error (Ulijaswek 1999, Cogill 2003). To check the accuracy of the measurements, a different member of the study team will repeat 10% of measurements on the same day.

#### **3.6.3. Water quality**

Thermotolerant coliforms will be used as an indicator of faecal contamination in drinking water samples (WHO 1993). Each month, a random sample of 20% of households will be selected. Field staff will conduct unannounced visits and take a sample from the storage vessel designated as containing the child's drinking water. All samples will be collected in sterile 100ml Whirl-Pak bags with a tablet of Thio-Sulfate to inhibit any disinfectant. Samples will be transported to the lab in coolers and analysed within 4 hours. Microbiological assessment will be performed using the membrane filtration technique on membrane lauryl sulphate medium (Oxoid Limited, Basingstoke, Hampshire, UK) using a DelAgua field incubator (Robens Institute, University of Surrey, Guilford, Surrey, UK) in accordance with the kit's instructions.

#### **3.6.4. Compliance**

Compliance will be assessed in two ways: 1) by asking the respondent (primary care giver of the child) if the child's drinking water has been treated and if so, the method that was used 2) by measuring presence of residual free chlorine in household water storage container. Chlorine testing will be conducted in a similar way in control and intervention households. Measuring chlorine in the control arm will help assessing neutrality of the placebo tablets and monitor any potential contamination due to exchange of the tablets between households. Concentration of free chlorine in the water will be measured to monitor dosage levels among intervention households. Chlorine will be assessed using a colorimetric indicator and DPD1 reagent (Palintest Limited).

#### **3.6.5. Cost savings and school absenteeism**

We will use surveys of participating households to collect information on health care expenditures for diarrhoea, both to determine any cost savings that might incur to households by using the intervention (reduced expenditures on drugs and healthcare) and as a further objective outcome associated with the intervention. We will also determine the impact of the intervention on absenteeism from school through household survey each month, roll calls in study village schools, and registers.

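### Household cost savings are measured from spending that the trial's own free care partly replaces, so the absolute saving is modestly understated if the tablets work

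*Protocol*

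**What the plan says.** Protocol section 3.6.5 sets out the cost outcome: "We will use surveys of participating households to collect information on health care expenditures for diarrhoea". The data have two uses. The first is "to determine any cost savings that might incur to households by using the intervention (reduced expenditures on drugs and healthcare"). The second is "as a further objective outcome associated with the intervention". The section gives no recall period for the expenditure questions and no rule for items that the household received without paying.

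Section 3.6.1 describes what happens when a visit finds a sick child: "Children found to suffer from diarrhoea will be given oral rehydration sachets and instructions on how to use them". It continues: "If required, they will be referred to the closest community health centre to receive medical care free of charge". No distinction by arm is made. On timing, the same section says: "The follow-up will be conducted monthly over 12 months".

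Section 2 lists "the cost-effectiveness of the intervention" as secondary objective (vii). Sections 3.6.1 and 3.6.5 do not refer to each other, and neither says that trial-supplied ORS or referral care will be recorded, valued or kept apart from the spending comparison.

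**The concern.** The quantity of interest is what a household would save by using the tablets. Outside the trial, no study visitor would arrive each month with sachets and a free referral. Inside it, some of what a household would have bought for a sick child is handed over, so the survey records spending after a subsidy.

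The subsidy follows episodes. If the tablets work, the control arm has more episodes and receives more of it, so more spending is removed there than in the intervention arm. A saving is an absolute difference between arms, and that difference shrinks. A cost-effectiveness figure that deducts household savings from programme cost would inherit the shortfall.

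The issue has to be met during follow-up. An analysis plan cannot value sachets or referrals that nobody wrote down.

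**Working it through.** The protocol gives no unit cost, expected saving or precision for this outcome, so there is no stated figure to reproduce. The check is on the size of the effect.

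**Inputs from the protocol**
- Visits: monthly for 12 months (3.6.1), so 365/12 = 30.4 days apart.
- Control prevalence 4% and a 15% relative reduction (3.8).

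**Assumptions, because the protocol is silent**
- Episode length d = 3, 4 or 5 days.
- The expenditure questions cover all episodes, not only those found at a visit.
- Episodes have similar length and cost in both arms, and spending is spread evenly over the days of an episode.

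**Step 1. Share of episodes under way on a visit day** = d/30.4.
- d = 3: 9.9%
- d = 4: 13.2%
- d = 5: 16.4%

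If trial care removed all spending on these episodes, the absolute saving would be understated by the same share. This is the upper limit for visit-day supplies.

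**Step 2. Only spending from the visit day onward can be replaced.** The visit falls on a random day of the episode, so the average share of spending still to come, counting the visit day, is (d+1)/(2d).
- d = 3: 4/6 = 0.67, and 9.9% x 0.67 = 6.6%
- d = 4: 5/8 = 0.63, and 13.2% x 0.63 = 8.2%
- d = 5: 6/10 = 0.60, and 16.4% x 0.60 = 9.9%

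**Step 3. Half of that spending is replaced**, since ORS is only part of what families buy: 3.3%, 4.1% and 4.9%.

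**Step 4. Example in cost units.** Take d = 5 and 100 units per episode.
- Control episodes per child-year: 0.04 x 365/5 = 2.92. Intervention: 2.92 x 0.85 = 2.48.
- True saving: 2.92 x 0.15 x 100 = 43.8 units.
- Observed under step 1: 43.8 x (1 - 0.164) = 36.6.
- Observed under step 2: 43.8 x (1 - 0.099) = 39.5.
- Observed under step 3: 43.8 x (1 - 0.049) = 41.6.

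**Step 5. Ratio of arms.** The same fraction f is removed in each arm, so the ratio is 2.48(1 - f)/2.92(1 - f) = 0.85 whatever f is. With no true effect, the difference is zero with or without the subsidy.

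**The case against.** The strongest reply is that this is a small, conservative distortion of one secondary outcome. Arms are randomised, blinded and treated alike, so the ratio of spending is sound, and spending used as a further outcome of effect remains a valid comparison between arms. That stands. It limits the point to the absolute saving.

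A reader might infer that episodes found by the study cost the household almost nothing. The protocol does not support this. Only ORS goes to every child found ill, and referral depends on need. Spending before the visit, on other drugs, on other providers or on travel is untouched.

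A reader might also count every episode that touches the 3-day recall window, which gives (d+2)/30.4, or 16-23% for 3-5 days. But section 3.6.1 gives ORS to children found to be ill. It does not say that a child who has already recovered receives any, so the visit-day figures fit the text better.

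Three further points stand in part:
- Section 3.6.1 does not say whether the trial pays for referral care or the health centre is free anyway. If it is free anyway, pricing that care would overstate the saving. The fix has to respect this.
- No section says that the spending data enter objective (vii), so bias in the cost-effectiveness result is conditional on how that result is built.
- Section 3.6.5 speaks of households. Unsubsidised spending on older members would dilute the effect if it is counted.

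The last argument is that valuation belongs in an analysis plan. That is fair for pricing, but not for logging, which must happen at the visits. Reuse of leftover sachets could add to the effect, but no quantity is given, so it is not counted here.

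**Conclusion.** The point holds in a limited form. Reported spending is partly net of care that the trial arranges, and if the tablets reduce diarrhoea the absolute household saving is biased modestly toward zero. For assumed episodes of 3-5 days, the understatement from visit-day supplies is at most 10-16%, about 7-10% if only spending from the visit day onward is replaced, and about 3-5% if half of that is.

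These figures rest on assumed episode length, even spending over an episode, and expenditure questions that cover all episodes. They would be larger if the questions cover only episodes found at visits, which the unstated recall period leaves open. The primary outcome is not affected. This is a minor to moderate weakness in a secondary economic outcome, worth correcting because it is cheap to do.

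**What to change.** Leave the care given to children as it is, and make four changes:

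1. On the monthly form, log by child the number of ORS sachets supplied and whether a referral was used.
2. In section 3.6.5, state the recall period of the expenditure questions.
3. Report out-of-pocket spending as planned. Alongside it, report a total that adds trial-supplied ORS at local prices, and adds referral care at local prices only where the household would have paid for it outside the trial.
4. Use the adjusted total in any cost-effectiveness calculation that nets off household savings.

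The cost is two form fields, a local price list and one extra line of analysis. The downside is that the added component relies on assumed local prices. Reporting both totals lets the reader see how much depends on them.
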